8.1 Study Drug and Materials

8.1.1 Dosage Form, Manufacturing, Packaging, and Labeling

In this protocol, the term study drug refers to all or any of the drugs defined below.

- Commercial vortioxetine tablets in encapsulated strengths of 10 and 20 mg.
- Commercial paroxetine tablets in encapsulated strength of 20 mg.
- Matching placebo capsules.

Vortioxetine 10 and 20 mg tablets are manufactured by Takeda or H. Lundbeck A/S, Valby, Denmark. Overencapsulation of the vortioxetine and paroxetine tablets and manufacturing of the matching placebo capsules (Swedish-Orange capsules with lactose monohydrate filler) is performed by Almac Clinical Services, Souderton, PA, USA.

The study drug will be packaged in high-density polyethylene bottles with child-resistant closures. Each bottle contains 7 daily doses plus 3 extra capsules for a total of 10 capsules per bottle. The daily dose is 1 capsule by oral administration.

Bottles of overencapsulated (OE) vortioxetine 10 and 20 mg tablets, OE paroxetine 20 mg tablets, and matching placebo capsules will be labeled with a single label and dispensed as double-blind for the 5-week treatment phase. The study drug will be identifiable by a unique medication identification (ID) number that will be assigned by an interactive web response system (IWRS). Each bottle will be labeled with pertinent study information.

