8.1.3 Dose and Regimen

The investigator or designee should contact the IWRS to register each subject at the initial Screening Visit. At each applicable study visit (Visits 1-5), the investigator or designee should contact the IWRS to receive the appropriate study drug assignment for dispensation. The IWRS will provide the medication ID number for each bottle dispensed at each study visit. The medication ID number assigned should be recorded in the source document.

Subjects assigned to vortioxetine 20 mg will initiate treatment at 10 mg/day for the first week. Subsequently, the dose will be increased to 20 mg/day and remain at 20 mg/day until study completion. Subjects assigned to vortioxetine 10 mg will initiate treatment at 10 mg/day and remain at 10 mg/day until study completion. Subjects assigned to paroxetine 20 mg will initiate treatment at 20 mg/day and remain at 20 mg/day until study completion.

Subjects will be instructed to take 1 capsule per day, orally, at the same time of day, preferably in the morning, or as directed. The first dose is to be taken on Day 1, the day after the study drug has been dispensed to the subject. Study drug can be taken with or without food. The subject should be advised to be consistent in the dosing time throughout the duration of the study.

The investigator or designee will instruct the subject on the dosing procedures and study drug storage requirements. Subjects should return their unused study drug at each study visit to allow the investigator or designee to evaluate subjects' compliance with the dosing instructions.

The daily dose and capsule count that will be provided to each treatment group is described in [Table 8.a.](#)

Table 8.a Dose and Regimen

Treatment Group	Dose	Treatment Description
A	Placebo QD	1 placebo capsule
B	10 mg vortioxetine QD	1 OE vortioxetine 10 mg tablet
C	20 mg vortioxetine QD	1 OE vortioxetine 20 mg tablet
D	20 mg paroxetine QD	1 OE paroxetine 20 mg tablet

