9.2 Monitoring Subject Treatment Compliance

A digital compliance technology will be implemented in this study, as described below. Subjects will also be required to bring study drug containers to each clinic visit, regardless of whether the study drug container is empty.

Subjects will be monitored for compliance using AiCure's artificial intelligence platform. The technology will be provided as a smartphone application. Subjects will use the smartphone application to monitor themselves taking the study drug. Subjects will either download the application to their own smartphone, or for subjects who do not have a smartphone or who do not wish to download the application to their own device, a smartphone-like device will be issued to them and must be returned at the end of their participation in the study. The Health Insurance Portability and Accountability Act (HIPAA)-compliant artificial intelligence software is able to identify and confirm the subject, the study drug, and ingestion of the study drug.

The subjects will monitor themselves taking the study drug using the application each time they take the study drug during the study. At the required dosing time, the software provides a reminder and takes the subject through a multistep process: (1) subject identification; (2) study drug identification; (3) confirmation that the subject has placed the study drug in his or her mouth. After determination of medication adherence by the smartphone application, data captured will be encrypted and transmitted to a secure, centralized, web-based dashboard, which the study site can access through a roles-and-rules-restricted, HIPAA-compliant system. When a subject is initially registered, a residential and/or mobile phone number will be encrypted and stored onto the dashboard. Subjects will also be able to manually enter into their device at a later time period if they took study drug but did not have their device on them, or if it was not working at the time.

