(g) PTEs to be assessed from the date of Screening up to the first dose of study drug on Day 1.

(h) AEs to be assessed daily from the first dose of study drug on Day 1 until the Follow-up Contact at Week 7.

(i) Serum test at Screening and urine test at all other visits. For women of child-bearing potential only.

(j) The subject should complete the CSFQ-14 before the PGI-I.

(k) Six PK blood samples to be collected for each subject (2 samples at each time point at Weeks 3, 4, and 5/ET) for measurement of plasma vortioxetine or paroxetine concentrations. At Week 5/ET, the blood sample will be collected at the same time point as the blood sample for clinical laboratory tests. Subjects will be instructed to take the study drug immediately after collection of the PK blood sample.

(l) One 6-mL whole blood sample to be collected for DNA isolation predose at Baseline (Day 0) from each subject.

(m) Two 2.5-mL whole blood samples to be collected for RNA isolation predose at Baseline (Day 0) and also at Week 5/ET from each subject (ie, 4 samples per subject).

(n) Subjects are to be instructed to take the first dose of study drug on the morning of Day 1 (morning after Baseline).

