Adverse events that start more than 30 days after the last dose of double-blind study medication (start date – last dose date >30) will be listed, but excluded from the summaries and analyses. For efficacy and other safety data, data that are obtained more than 7 days after the last dose of double-blind study medication (visit date – last dose date >7) will be listed, but excluded from summaries and analyses. For certain safety measurements such as laboratory tests, summary statistics for the last visit will be presented, which will display values closest to the last dose of the double-blind medication within the cutoff day for that variable.

If the date of the first double-blind dose is missing due to the subject being lost to follow-up after being dispensed drug then the first dose dispensed date + 1 day will be used for analysis and summary purposes. Similarly, if the date of last double-blind dose is missing, then the date of the last double-blind drug dispense date + (the last number of doses dispensed – the last number of doses returned) - 1 will be used.

The study window convention will not be applied to the eCRF data listings. The data listings for eCRF data will display the raw data as collected and entered in the eCRF. For CSFQ-14 and PGI-I, windowed visits will be shown on the listings.

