7.2 Major Protocol Violations

All subjects with major protocol violations will be identified in the minutes of the subject evaluability assessment performed prior to unblinding, and will be listed by study center and subject number.

Subjects with the following major protocol violations will be excluded from the per protocol set (PPS):

- No evaluable baseline CSFQ-14 assessment.
- No evaluable post-baseline assessment of CSFQ-14.
- Low study drug compliance (<70%) or missed study drug for 4 consecutive days.
- Double-blind study medication exposure less than 7 days (last dose date – first dose date +1 <7).
- Subjects switch treatment during study.

Other major protocol violations will be identified by the study team prior to unblinding.

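### The SAP's formula for a missing last-dose date is one day short when Baseline was the last dispensing, because dosing starts the day after (minor)

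*SAP*

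**What the plan says.** SAP 7.1.3 gives two imputation rules in one paragraph. If the first-dose date is missing because the subject was lost to follow-up after being given drug, then "first dose dispensed date + 1 day will be used for analysis and summary purposes". If the last-dose date is missing, the SAP takes the last dispense date and adds the capsules unaccounted for, less one: "the last number of doses dispensed – the last number of doses returned) - 1 will be used".

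The protocol fixes the start of dosing for the Baseline bottle. Section 8.1.3 states: "The first dose is to be taken on Day 1, the day after the study drug has been dispensed to the subject". Footnote (n) of Appendix A agrees. Section 8.1.1 states: "The daily dose is 1 capsule by oral administration".

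The imputed date is then used in several places:
- SAP 7.8 computes exposure and percent compliance from it.
- SAP 7.2 lists "Double-blind study medication exposure less than 7 days" among the violations that remove a subject from the per-protocol set (PPS).
- SAP 7.1.3 excludes from summaries and analyses efficacy data obtained more than 7 days after the last dose, and adverse events starting more than 30 days after it.

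**The concern.** The two rules are presented as parallel but count from different days. The first puts the first capsule on the day after dispensing. The second is right only if the first capsule from the last bottle is taken on the dispensing day itself, which the protocol rules out for the Baseline bottle. A subject whose only bottle was the Baseline one is therefore given a last-dose date one day too early. At the extremes the dates become impossible, or the subject's per-protocol status changes.

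**Working it through.** **Inputs**
- D: Baseline dispense date. First dose is D + 1 (Protocol 8.1.3 and Appendix A footnote n; SAP 7.1.3).
- n: capsules dispensed minus capsules returned, taken one a day (Protocol 8.1.1). A bottle holds 10 capsules, of which 3 are spare.
- Imputed last dose: D + n − 1 (SAP 7.1.3).
- Exposure: last dose − first dose + 1 (SAP 7.2 and 7.8).
- Compliance: n / exposure × 100% (SAP 7.8).
- PPS exclusion: exposure below 7 days (SAP 7.2).

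The documents give no numerical result for this rule, so there is no figure to reproduce.

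**Baseline is the last dispensing**

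Taken as instructed, capsule 1 falls on D + 1 and capsule n on D + n.
- Exposure as instructed: (D + n) − (D + 1) + 1 = n.
- Exposure under the SAP rule: (D + n − 1) − (D + 1) + 1 = n − 1.
- Compliance under the SAP rule: n / (n − 1), where the subject was in fact 100% compliant.

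| n | Imputed last dose | Exposure, SAP rule | Exposure, as instructed | Compliance, SAP rule | Below 7 days: SAP rule / as instructed |
|---|---|---|---|---|---|
| 1 | D | 0 | 1 | 1/0, undefined | yes / yes |
| 2 | D + 1 | 1 | 2 | 200% | yes / yes |
| 5 | D + 4 | 4 | 5 | 125% | yes / yes |
| 6 | D + 5 | 5 | 6 | 120% | yes / yes |
| 7 | D + 6 | 6 | 7 | 116.7% | yes / no |
| 8 | D + 7 | 7 | 8 | 114.3% | no / no |
| 10 | D + 9 | 9 | 10 | 111.1% | no / no |

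With n = 1 the last dose falls on D, a day before the first dose on D + 1. With n = 5 a fully compliant subject lands in the SAP's top compliance category (120% or more). Only n = 7 changes PPS status.

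**Cut-offs**

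A CSFQ-14 obtained exactly 7 days after the true last dose is counted as 7 + 1 = 8 days and excluded. An adverse event starting exactly 30 days after it is counted as 31 days and left out of the summaries.

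**Later bottles**

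Take nominal dispensing on Days 0, 7, 14, 21 and 28 with 7 capsules used from each bottle. If each bottle is started the next day, the last doses fall on Days 7, 14, 21, 28 and 35. The SAP rule gives Days 6, 13, 20, 27 and 34. A nominal completer whose date had to be imputed would show 34 days of exposure and move from the category of 35 days or more to that of 28 to 34 days. If a bottle is started on the day it is dispensed, the SAP rule is correct for that bottle.

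**The case against.** A reader might infer that the rule is wrong for every bottle. The documents do not support that. They do not say outright whether a bottle dispensed after Baseline is started on the visit day or the next. Seven daily doses a week from Day 1 point to the next day. But at Weeks 3 and 4 drug is dispensed and the subject doses after the PK draw (Protocol 9.1.16.1), possibly from the new bottle, so subtracting 1 may be right there.

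A reader might also infer that early-termination CSFQ-14 scores are lost from the primary analysis, which carries the last score forward. For that, the score would have to fall on the one day affected by the shift and the last-dose date would have to be missing. Yet withdrawn subjects have Final Visit procedures, which include PK sampling, and at PK visits the date and time of the previous dose go on the eCRF. A subject with an early-termination score should therefore normally have a last-dose date.

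The extreme cases are narrow too. They need a missing date, a known return count and no dispensing after Baseline, and returns are counted at visits, where a last-dose date would usually be obtainable. If the return count is missing, SAP 7.8 assigns 100% compliance. PPS analyses run only if more than 5% of the FAS have major violations, and only for the primary variable; exclusions are settled before unblinding, so a seven-capsule case could be noticed.

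Missed days are not an arithmetic error in the SAP. They make any capsule-count date too early, and lost capsules make it too late.

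The compliance application might look like the obvious source of dates, since "The subjects will monitor themselves taking the study drug using the application each time they take the study drug during the study". But doses can be entered manually later, and the protocol describes a site dashboard, not a transfer to the analysis database.

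All of this limits the reach of the point. None of it reconciles the two rules for the Baseline bottle.

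**Conclusion.** The point holds for the Baseline bottle: as written, the rule gives a last-dose date one day early, an impossible date order at one capsule, and a wrong PPS exclusion at seven. This assumes one capsule a day from Day 1 with none missed or lost. For later bottles the shortfall is likely under the nominal schedule but not established.

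The documents do not say how many subjects will have a missing last-dose date with a known return count; few is a reasonable expectation. The FAS primary analysis has no 7-day exposure limit, and no effect on the primary result is shown. Severity is minor: a stated fallback rule gives a wrong answer and is easily corrected.

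**What to change.** Before unblinding, replace the last-dose sentence in SAP 7.1.3 with: *If the last-dose date is missing, use the last dispense date + (doses dispensed − doses returned), not earlier than the first-dose date; subtract 1 only where the eCRF shows that a capsule from that bottle was taken on the dispensing day.*

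For the Baseline bottle, one capsule then gives D + 1 and 1 day of exposure. Seven give D + 7 and 7 days, so the subject stays in the PPS. Compliance is 100% in both cases. A nominal fifth bottle gives 28 + 7 = Day 35.

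The cost is one SAP sentence. Subjects with a recorded last-dose date are unaffected. Two weaknesses remain. The eCRF records the dose taken at PK visits, but the documents do not say that it records which bottle was used; a same-day start that is not shown there would be dated one day late. And a 10-capsule bottle with a return count of zero would give D + 10 instead of D + 9, so lost capsules still push the date late.

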7.1.4 Grouping of Centers

Before unblinding the data, centers that are considered small (<8 subjects) will be pooled with geographically similar centers to minimize artifacts in the statistical analyses from imbalances in subject counts within the centers.

The pooling of the centers will be reviewed and approved by the clinical team for agreement, and is then used in the appropriate analyses once the database is locked and unblinded.

7.2 Major Protocol Violations

All subjects with major protocol violations will be identified in the minutes of the subject evaluability assessment performed prior to unblinding, and will be listed by study center and subject number.

Subjects with the following major protocol violations will be excluded from the per protocol set (PPS):

- No evaluable baseline CSFQ-14 assessment.
- No evaluable post-baseline assessment of CSFQ-14.
- Low study drug compliance (<70%) or missed study drug for 4 consecutive days.
- Double-blind study medication exposure less than 7 days (last dose date – first dose date +1 <7).
- Subjects switch treatment during study.

Other major protocol violations will be identified by the study team prior to unblinding.

7.3 Analysis Sets

The safety set will include all subjects who were randomized and received at least 1 dose of double-blind study medication. In safety summaries, subjects will be analyzed according to the treatment they received. In the event that a subject receives more than 1 treatment, the actual treatment will be defined as the 1 that is used most frequently. If the 2 most common treatments are used with equal frequency, then the randomized treatment will be used as the actual treatment.

The full analysis set (FAS) will include all subjects who were randomized, received at least 1 dose of study drug, and had at least 1 valid post-baseline value for assessment of primary efficacy. In FAS efficacy summaries, subjects will be analyzed by the treatment to which they were randomized.

To adjust for treatment noncompliance, two modified FAS populations, mFAS1 and mFAS2, will be defined based on the PK data. The mFAS1 excludes subjects in the vortioxetine treatment

CONFIDENTIAL

arm who had drug concentration below the limit of quantification at all study visits where PK is collected, while the mFAS2 excludes subjects in the vortioxetine treatment arm who had drug concentration below the limit of quantification at any study visit where PK is collected. The PPS will include all FAS subjects who had no major protocol violations. If more than 5% of the total subjects in the FAS have major protocol violations, analyses based on the PPS will be performed for the primary efficacy variable only.

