6.2 Justification for Study Design, Dose, and Endpoints

6.2.1 Study Design

Healthy adult subjects were chosen for inclusion in this study to eliminate the confounding effects on sexual function associated with psychiatric conditions and certain medical conditions. The duration of 5 weeks was selected to allow for sufficient time to evaluate the extent of sexual dysfunction.

Paroxetine was chosen as an active comparator as it is a commonly prescribed SSRI and is known to cause sexual dysfunction, thereby allowing for validation of the study (ie, the level of sexual dysfunction with paroxetine is worse than that of placebo). The level of sexual dysfunction with vortioxetine 10 and 20 mg will also be compared with placebo.

Since study drug compliance is known to impact the study results, a compliance technology vendor, AiCure, will be used to throughout the study to improve study drug compliance. In addition, PK samples will be taken at 3 postbaseline study visits in order to assess plasma concentrations of vortioxetine and paroxetine. The compliance technology and/or PK concentration data will be used to define one or more modified full analysis set populations.

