9.1.16 PK Sample Collection and Analysis

9.1.16.1 Collection of Plasma for PK Sampling

A total of six 6-mL PK blood samples (trough samples) will be collected from each subject at 3 separate study visits (2 samples at each time point at Weeks 3, 4, and 5/ET). At Week 5/ET, the blood sample will be collected at the same time point as the blood sample for clinical laboratory tests. Subjects will be instructed to take the study drug immediately after PK blood samples are collected. The exact date and time of last dose prior to the scheduled PK visit as recorded on the subject diary, the exact time of PK blood draws, and the exact time of dose taken at the site at the PK visit will be recorded on the appropriate eCRF.

Please refer to [Appendix E](#) for instructions for the collection, handling, and shipping of plasma samples for PK analysis. Samples collected from subjects in the vortioxetine and paroxetine groups will be analyzed by the bioanalytical laboratory to measure vortioxetine and paroxetine concentrations in plasma, respectively. Samples collected from subjects in the placebo groups will not be analyzed. The bioanalytical laboratory will be unblinded to select the subjects receiving vortioxetine or paroxetine.

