7.9.3 Primary Efficacy Endpoint(s)

Mean change from Baseline in the CSFQ-14 total score difference for vortioxetine vs paroxetine after 5 weeks of treatment will be the primary endpoint. The primary analysis will be based on analysis of covariance (ANCOVA) using the last observation carried forward (LOCF) technique, with treatment, center, and sex as fixed factors, and baseline CSFQ-14 total score as covariate. The comparisons will be between each vortioxetine dose (10 or 20 mg) and paroxetine, and both statistical tests will be 2-sided.

The following example SAS code will be used for the ANCOVA analysis:

```
Proc mixed data=all;
  - class treat center sex;
  - model Change= Baseline treat center sex;
  - lsmeans treat;
```

In the above model, Baseline is the baseline value and Change is the change from baseline value.

The Holm-Bonferroni method will be used to adjust for multiplicity and control the familywise type I error rate at a significance level of 0.05. If the smaller of the 2 P-values is <0.025 , significance is obtained for the associated vortioxetine dose and the other dose will then be evaluated at a 0.05 significance level. Although vortioxetine will be compared with paroxetine in the primary analysis, paroxetine will also be compared with placebo to validate the study. The primary analyses will also be repeated based on the PPS if more than 5% of the total subjects in the FAS have major protocol violations.

As supportive analyses, the sex-by-treatment interaction term will be added to the primary analysis model to further check the sex effect on the treatment. The similar ANCOVA analyses will also be performed using the observed case (OC) data.

Change from Baseline in the CSFQ-14 total score will also be analyzed based on a mixed model for repeated measurements (MMRM) with treatment, center, week, treatment-by-week interaction and sex, as fixed effects, and baseline CSFQ-14 total score, and CSFQ-14 total score-by-week as covariates. The effect at each time point for each treatment is allowed to vary freely and an unstructured covariance matrix is assumed.

The SAS code for the MMRM analysis will be as follows:

```
Proc mixed data=all;
  - class week treat center subject;
  - model Change = baseline*week baseline treat center week week*treat sex /solution;
  - repeated week/subject=subject type=UN;
  - lsmeans week*treat / cl pdiff.
```

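### The PK-based noncompliance sets (mFAS1, mFAS2) filter the vortioxetine arms but not paroxetine, so they cannot remove noncompliance from the main contrast

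*SAP*

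**What the plan says.** Protocol 6.2.1 states that compliance affects the results of such studies and that PK samples are taken to assess both active drugs. It then says: "The compliance technology and/or PK concentration data will be used to define one or more modified full analysis set populations". Protocol 13.1.1 repeats that modified full analysis sets will adjust for noncompliance. Neither section restricts the adjustment to particular arms.

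SAP 7.3 makes this concrete: "To adjust for treatment noncompliance, two modified FAS populations, mFAS1 and mFAS2, will be defined based on the PK data". Its first rule begins "The mFAS1 excludes subjects in the vortioxetine treatment" and applies to subjects below the limit of quantification at all PK visits. Its second rule follows: "while the mFAS2 excludes subjects in the vortioxetine treatment arm who had drug concentration below the limit of quantification at any study visit". Neither rule mentions paroxetine.

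On what is assayed, Protocol 9.1.16.1 says "Samples collected from subjects in the vortioxetine and paroxetine groups will be analyzed by the bioanalytical laboratory", and of placebo, "Samples collected from subjects in the placebo groups will not be analyzed".

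SAP 7.9 bases the efficacy analyses on the FAS. SAP 7.9.3 makes each vortioxetine dose vs paroxetine the primary comparison and adds a conditional per-protocol repeat: "The primary analyses will also be repeated based on the PPS if more than 5% of the total subjects" in the FAS have major violations. Sections 7.9.3 to 7.9.5 assign no analysis to mFAS1 or mFAS2.

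**The concern.** A set meant to adjust for noncompliance should treat both sides of the comparison alike wherever the data allow. Here the trial's main contrast is between two assayed drugs, and only one of them is filtered. Vortioxetine subjects without measurable drug leave; paroxetine subjects without measurable drug remain and keep diluting the paroxetine effect.

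The risk is one of interpretation. If a vortioxetine vs paroxetine result on mFAS1 or mFAS2 agrees with the FAS, a reader may conclude that noncompliance did not matter, when the set may have been unable to show that it did. Because no analysis is tied to either set, their use is also left open until after unblinding.

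**Working it through.** **The plan's own figures (background, not in dispute).** SAP 6.0 uses 88 per arm, SD 8.5, difference 4.0 and two-sided 0.025. The noncentrality is 4.0 / (8.5 × √(2/88)) = 3.12. Power is 80.4% by the noncentral t with 174 df and 81.1% by the normal approximation, against the stated 80% or more. Simulating the Holm procedure (400,000 trials, shared paroxetine arm, both true differences 4.0) gives 85.3% per dose, against the stated 85% or so.

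**Which arms can be filtered.**

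| Arm | Assayed (Protocol 9.1.16.1) | Filtered in mFAS1/mFAS2 (SAP 7.3) |
|---|---|---|
| Vortioxetine 10 and 20 mg | Yes | Yes |
| Paroxetine 20 mg | Yes | No |
| Placebo | No | Not possible on PK |

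A one-sided rule is therefore forced for vortioxetine vs placebo, but not for vortioxetine vs paroxetine.

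**Size: model and assumptions.** The documents give no noncompliance rate and no drug vs placebo effect on the CSFQ-14, so these are assumed:
- ev and ep are the on-drug effects of vortioxetine and paroxetine vs placebo, with ev − ep = 4.0.
- q is the fraction excludable on PK, equal in each active arm.
- f is the share of drug effect that those subjects keep (0 for an mFAS1-type case, 0.5 for an mFAS2-type case).
- Excludable subjects are otherwise exchangeable with the rest.

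With k = 1 − q(1 − f):
- FAS difference = (ev − ep) × k
- One-sided set = ev − ep × k
- Symmetric set = ev − ep
- One-sided minus FAS = q(1 − f) × ev

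| Case | k | ev | ep | FAS | One-sided | Symmetric |
|---|---|---|---|---|---|---|
| q=10%, f=0 | 0.9 | +1 | −3 | 3.6 | 1 + 2.7 = 3.7 | 4.0 |
| | | 0 | −4 | 3.6 | 0 + 3.6 = 3.6 | 4.0 |
| | | −2 | −6 | 3.6 | −2 + 5.4 = 3.4 | 4.0 |
| q=20%, f=0 | 0.8 | +1 | −3 | 3.2 | 1 + 2.4 = 3.4 | 4.0 |
| | | 0 | −4 | 3.2 | 0 + 3.2 = 3.2 | 4.0 |
| | | −2 | −6 | 3.2 | −2 + 4.8 = 2.8 | 4.0 |

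The mFAS2-type case with q=20% and f=0.5 has k = 1 − 0.2 × 0.5 = 0.9, so it gives the same values as the first three rows.

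The last formula is the key one: the shift from the FAS depends only on vortioxetine's own effect against placebo. If that effect is zero, the one-sided set reproduces the FAS at any noncompliance rate. If vortioxetine lowers the score, the set moves away from 4.0.

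**Vortioxetine vs placebo, same model.** The FAS gives ev × k and the one-sided set gives ev. With q=20%, f=0 and ev = −2, that is −1.6 and −2.0, so the set does recover the on-drug effect here.

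**If excluded subjects differ in prognosis.** Suppose the drugs do not differ, but unquantifiable subjects differ from the others by s points in every arm. Filtering vortioxetine alone then creates a difference of −q × s. For q of 5% to 20% and s of ±2 to ±4, its absolute size runs from 0.05 × 2 = 0.1 to 0.20 × 4 = 0.8 points, in either direction.

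**The case against.** **No planned analysis uses these sets.** This is true, and the harm is conditional for that reason. But a set defined and left unassigned still needs a purpose before unblinding, and the natural use is the trial's main contrast.

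**The sets may be meant for vortioxetine vs placebo, or as a check that vortioxetine does not look benign merely because it was not taken.** This is the best defence. The set does recover the on-drug vortioxetine vs placebo effect, and where vortioxetine lowers the score the filter shrinks its advantage over paroxetine, so it does not flatter vortioxetine. The SAP states neither purpose, and the defence does not make the sets suitable for vortioxetine vs paroxetine.

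**The per-protocol set covers compliance.** It does so in part. SAP 7.2 applies one rule to all arms: "Low study drug compliance (<70%) or missed study drug for 4 consecutive days". Its listed criteria use no PK data, however, and the analysis runs only above the 5% trigger.

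**The size is small and rests on assumptions.** This stands. The tabulated shifts from the FAS are 0 to 0.4 points, against an FAS standard error of 8.5 × √(2/88) = 1.28. Much of the gap to 4.0 is ordinary dilution already present in the FAS. Protocol 4.2 and 6.2.2 describe vortioxetine as close to placebo on a different scale, which suggests a shift near zero. That is also the case in which agreement with the FAS says least about noncompliance.

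**Equal rules need not mean equal screening.** The two drugs have separate assays, and no quantification limits or elimination rates are given, so the symmetric 4.0 assumes that unquantifiable status identifies noncompliers equally well in both arms. The limitation is fair, but it applies to the SAP's own rule too.

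**Conclusion.** The point holds. SAP 7.3 filters one side of the main contrast when the data to filter both are already being collected, and it gives no reason. For vortioxetine vs paroxetine the sets cannot do the job stated for them.

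The consequence is confined to supportive analyses. The primary FAS estimate, type I error and sample size are unaffected. The illustrated size depends on assumed noncompliance rates, equal in both drugs, and on an assumed vortioxetine effect against placebo. No direction of bias can be claimed in general, because prognostic differences among excluded subjects could move the result either way. It should be corrected before unblinding.

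**What to change.** In SAP 7.3, apply one rule to every assayed arm: exclude subjects randomized to vortioxetine 10 mg, vortioxetine 20 mg or paroxetine 20 mg whose assigned drug is below quantification at all PK visits (mFAS1) or at any PK visit (mFAS2). State how FAS subjects with no PK sample are classified; sampling starts only at Week 3, and the SAP is silent on this.

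In SAP 7.9.3, state that the primary ANCOVA is repeated on both sets as a supportive analysis of vortioxetine vs paroxetine. Add two caveats:
- Placebo is not assayed, so PK-based contrasts with placebo remain one-sided. The smartphone compliance data in Protocol 9.2 are not limited to the assayed arms and could support a rule covering placebo if one is wanted.
- Even the symmetric set conditions on behaviour after randomization, so it does not replace the FAS result.

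If the one-sided rule is deliberate, say so and limit its use to vortioxetine vs placebo.

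The cost is SAP wording and one derived flag, since paroxetine is already assayed, plus fewer paroxetine subjects in a supportive analysis. With SE = 8.5 × √(1/n1 + 1/n2):
- q=10%: about 9 paroxetine subjects are removed, and the SE goes from 1.32 (79 vs 88) to 1.35 (79 vs 79).
- q=20%: about 18 are removed, and the SE goes from 1.36 (70 vs 88) to 1.44 (70 vs 70).
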